#### **10.3.4.4 Analysis of IPF DNA Markers**

Exploratory analyses will be performed to evaluate the relationship between clinical response to FG-3019 and variants in the chromosomal loci listed in Section 7.6.5

#### **10.3.5 Safety Analyses**

Treatment-emergent adverse events (TEAEs), defined as new or worsening AEs that occur after the first dose of study drug and within 4 weeks of last dose of study drug, will be tabulated to examine their frequency, severity, organ systems affected and relationship to study treatment. Treatment emergent SAEs and TEAEs leading to study or treatment discontinuation will be listed or tabulated separately.

Clinically significant changes from baseline in vital signs, laboratory tests, physical examinations, and ECGs will be identified.

Human anti-human antibody data will be summarized in a separate report.

#### **10.3.6 Interim Analyses**

Unblinded analysis of changes in pulmonary function and in pulmonary fibrosis will be performed after all subjects have either completed Week 48 assessments or discontinued the study early (prior to week 48 of the Randomized Treatment Phase). This analysis may be performed before data lock for the primary analysis of safety and efficacy provided the relevant pulmonary function and pulmonary fibrosis data are cleaned. If there is a substantial gap in completion of enrollment between subjects on first-line therapy and the pirfenidone and or nintedanib treatment failures, unblinded subgroup analysis may be performed at different times.

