**Figure 1. Study Schema**

#### 4.2.2 Randomized Treatment Phase

Treatment should begin within 42 days of the first screening visit. Study Drug (FG-3019 [30 mg/kg] or placebo) will be administered by IV infusion every 3 weeks for a total of 16 infusions over 48 weeks.

The schedule of assessments of safety and efficacy are provided in Appendix 1 and Appendix 2. Safety and tolerability will be monitored closely by FibroGen. Cumulative safety experience will be evaluated by FibroGen on a regular basis. Final efficacy assessment is in Week 48. Subjects who do not enter the Extended Treatment Phase will undergo end-of-study (EOS) assessment (Appendix 3) on Week 49 (4 weeks after last dose of study drug).

After all subjects complete Week 48 evaluations or prematurely discontinue the study, data will be cleaned and locked for the primary analysis of efficacy and safety.

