## 10 STATISTICS

### 10.1 Sample Size Determination

This study is planned to enroll approximately 136 subjects, which will include a target of 110 subjects who are seeking first-line therapy and 26 subjects who failed pirfenidone and/or nintedanib treatment. First-line therapy is defined as no prior therapy with pirfenidone/nintedanib or <10% relative decrease in FVC % predicted while receiving either pirfenidone or nintedanib. Failure of pirfenidone and or nintedanib treatment is defined as having  $\geq 10\%$  relative decrease in FVC % predicted during prior pirfenidone/nintedanib treatment. The effect of first-line treatment is the primary interest of the study, and is the basis for sample size determination. Assuming a 10% dropout rate and a common standard deviation of 7.3, a sample size of 55 subjects per arm in the primary analysis population provides approximately 80% power to detect a treatment difference of 4.2 in change from baseline to Week 48 in percent predicted FVC, using a two-sample t-test at the two-sided significance level of 0.05. The expected treatment difference is estimated using data from study FG-3019-049 and placebo data from published studies. In Study FG-3019-049, a mean decline of 2.8 in % predicted FVC from baseline to Week 48 was observed. The expected decline of 7.0 % predicted FVC in the placebo arm is estimated based on the weighted average of published studies ([Azuma, 2005](#), [Daniels, 2010](#), [Demedts, 2005](#), [King, Jr., 2008](#), [King, Jr., 2009](#), [King, Jr., 2011](#), [Meier-Kriesche, 2004](#), [Noble, 2011](#), [Noth, 2012](#), [Raghu, 2004](#), [Raghu, 2008](#), [Raghu, 2012](#), [Richeldi, 2011](#), [Taniguchi, 2010](#), [Zisman, 2010](#)).

Second line therapy patients are evaluated in an exploratory fashion. If the treatment effect in the pirfenidone/nintedanib failure group is similar to that in the general population, the two subgroups will be combined to achieve higher power.

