#### **10.3.4.1 Primary Efficacy Analysis**

The primary analysis will be to compare the treatment arms in change from baseline to Week 48 in FVC % predicted based on the FAS Population. A rank ANCOVA model will be used, with baseline FVC % predicted value as covariate, treatment group, stratification, and treatment by stratification interaction as fixed effects. Factors may be eliminated from the model if they are insignificant. If the interaction term is significant, the primary analysis will be based on the subgroup of subjects on first-line therapy.

The ranks of the primary endpoint will be based on observed data and on imputed data if observed data are not available. A detailed description of the rank assessment will be described in the statistical analysis plan. A repeated measures model utilizing all observed data will be used for sensitivity analysis.

Descriptive summaries of the primary efficacy parameter will include the following:

1. Median change from baseline by treatment and visit
2. % of subjects with no decline by treatment and visit
3. % of subjects with decline  $\geq 10\%$  by treatment and visit

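### Week 48 FVC and HRCT may be compared by arm before the primary data lock, with event data unfrozen and the two subgroups unblinded at different times

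*Protocol*

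**What the plan says.** **Timing.** Protocol 10.3.6 (Interim Analyses) plans an unblinded analysis of pulmonary function and fibrosis once every subject has completed Week 48 or stopped early. On its relation to the lock it says: "This analysis may be performed before data lock for the primary analysis of safety and efficacy". The one condition is that the relevant lung-function and fibrosis data are clean. If the two subgroups finish enrolling far apart, each may be unblinded at its own time.

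**Lock.** Protocol 4.2.2 says that after all Week 48 visits or discontinuations "data will be cleaned and locked for the primary analysis of efficacy and safety".

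**Endpoints.** Week 48 change in FVC % predicted is primary (3.2.1). HRCT score, IPF progression, respiratory hospitalization and respiratory death are secondary (3.2.2). The progression analysis (10.3.4.3) counts death, a confirmed FVC fall not attributed to intercurrent illness, and a clinical diagnosis of progression.

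**Model and population.** Section 10.3.4.1 says "Factors may be eliminated from the model if they are insignificant". It moves the primary analysis to first-line subjects if the treatment-by-stratum interaction is significant. Section 10.1 pools the subgroups if their effects are similar. None of these rules has a stated threshold.

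**Safeguards and use.** Section 4.4.2 blinds subjects, site staff, the Medical Monitor and Clinical Operations. Section 4.4.3 limits planned efficacy unblinding to group level and keeps investigators and study teams blinded to the end. Under Section 9, a finding of no efficacy at the interim ends the extension.

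**SAP.** The available SAP is Part 2 (extension). Its Introduction places the randomized-period analyses in Part 1, which was not available for this review.

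**The concern.** Although labelled an interim, this analysis uses the complete Week 48 data for the primary endpoint. Two things can follow if it runs before lock.

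First, several outcomes that support the primary result depend on judgement: whether an FVC fall was due to intercurrent illness, whether IPF progressed clinically, and whether an admission or death was respiratory. They can still be queried and changed after a by-arm result exists. Even with no misconduct, the sponsor could not show that later edits were made without knowledge of the result.

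Second, with staggered unblinding the first-line result could be known while treatment-failure data are still accruing, and so before the decision to pool or to switch population. Group-level results are all that is needed to influence that decision.

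**Working it through.** **1. The plan's own power figure.** Inputs from Protocol 10.1: "Assuming a 10% dropout rate and a common standard deviation of 7.3"; "a sample size of 55 subjects per arm in the primary analysis population"; "approximately 80% power to detect a treatment difference of 4.2 in change from baseline to Week 48"; "using a two-sample t-test at the two-sided significance level of 0.05".

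- Evaluable per arm: 55 × 0.9 = 49.5.
- Standard error: 7.3 × √(2/49.5) = 1.467. Ratio: 4.2 / 1.467 = 2.862.
- Normal power: Φ(2.862 − 1.960) = Φ(0.902) = 81.7%. Noncentral t: 80.9%.
- Required n per arm (normal): 2 × (1.960 + 0.842)² × 7.3² / 4.2² = 47.4, so 48. With dropout, 48 / 0.9 = 53.3, so 54 against the stated 55.

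The stated figure is reproduced. The fix below leaves every input to it unchanged.

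**2. What must be clean when arm results are produced.**

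| Data | Used in | Covered by the 10.3.6 condition? | Judgement involved? |
|---|---|---|---|
| FVC values, including repeat spirometry | Primary endpoint; progression | Clean, not locked | Little |
| HRCT fibrosis score | Secondary | Clean, not locked | Some |
| FVC fall due to intercurrent illness or not | Progression | No | Yes |
| Clinical diagnosis of progression | Progression | No | Yes |
| Respiratory cause of admission or death | Secondary | No | Yes |
| Date and fact of death | Progression | No | No |
| Disposition and dropout reason | Possibly imputation | No | Some |
| Adverse events | Safety | No | Severity and relatedness |

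Under 10.3.4.1 the primary ranks use imputed values where observations are missing. If the imputation rule depends on death or dropout, unfrozen disposition data could also move the primary result. That is an assumption, because the rule is left to the SAP.

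**3. Scale of the population choice.** Protocol 10.1 gives "a target of 110 subjects who are seeking first-line therapy and 26 subjects who failed pirfenidone and/or nintedanib treatment", 136 in total. Under the null, with equal variances and 1:1 allocation, the first-line and pooled test statistics correlate at √(110/136) = 0.90. Each is tested at two-sided 5%.

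| How the population is chosen | Type I error |
|---|---|
| One population fixed in advance | 5.0% |
| Interaction rule followed mechanically, assumed pretest level 0.05 to 0.20 | 5.5% to 6.0% |
| Better of the two tests, chosen freely after results | 7.0% |

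The second row comes from 1,000,000 simulated trials; the third agrees with the exact bivariate normal value. Holding 5% under free choice would need a critical value of 2.109 (nominal 0.035).

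**4. Adding the model terms.** In 20,000 simulated rank-ANCOVA trials, with 50 first-line and 12 failure subjects per arm and an assumed baseline–outcome correlation of 0 to 0.4, the smallest p-value over the covariate choices gave 5.4% to 6.9%. Taken over covariates and population together it gave 7.5% to 9.7%. Simulation error is about 0.2 points.

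**5. What these numbers do not measure.** The 5.5% to 6.0% arises with or without a lock. The free-choice figures are worst cases, not the plan. No figure here measures the bias from editing event data; the documents give nothing from which to estimate it.

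**The case against.** The case on the other side is substantial.

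- **The early look has a purpose.** Section 9 ties it to ending the extension, and 10.3.1 ties study completion to it. Waiting for a full lock could delay that decision while extension subjects are still being dosed. This stands, and it is why the early look should not simply be deleted.
- **Blinding safeguards exist.** Efficacy unblinding is by group, sites and study teams stay blinded, and 12.4.2 has investigators verify data in an audit-trailed database. Steering an individual query towards one arm would need that subject's assignment. This stands in part. Section 4.4.2 does not name statistics or data management as blinded, and 4.4.3 does not define the study teams. Section 4.4.3 also has sponsor personnel unblind each subject after Week 48 and sends extension eligibility to sites. All placebo subjects are offered the extension (4.2.3.3), but amendment-enrolled active subjects only if FVC exceeds baseline (4.2.3.2). For those enrolled under an amendment, an offer made with FVC at or below baseline therefore points to placebo.
- **A lock freezes data, not a model.** The rules in 10.3.4.1 are applied to unblinded data either way. This stands: only an analysis plan fixed before unblinding closes that route.
- **SAP Part 1 may already fix the model, windows, imputation and pooling.** It may. The gap is shown for the protocol only.
- **Not every event is soft.** All-cause death is objective and FVC falls need repeat spirometry. This stands. The exposure lies in attribution and clinical diagnosis.

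**Conclusion.** The concern holds in a limited form. Section 10.3.6 expressly permits by-arm results on the primary endpoint's full Week 48 data before lock, requires nothing of the event, disposition or safety data, allows staggered subgroup unblinding, and does not say who receives the results. The safeguards in 4.4.2 and 4.4.3 reduce the risk but do not remove it.

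The effect on event endpoints cannot be quantified. For the population choice the worst case is 7.0% type I error against 5%, assuming the 110/26 split and free choice after seeing results.

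A reader might infer more than the documents support:

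- **That nothing in the trial needs the early look.** Section 9 gives its use.
- **That 10.3.6 contradicts 4.2.2.** It does not. It refers to the same lock and allows a separate analysis before it; 4.2.2 simply does not mention that analysis.
- **That the study team is known to see arm results before lock.** Sponsor access follows by inference from 4.4.3 and Section 9; recipients are not named.
- **That locking would by itself settle the model.** It would not, and Part 1 may already do so.

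This should be changed because the protection is cheap. It is not evidence that the primary result would be biased.

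**What to change.** 1. Amend 10.3.6 so that, before any by-arm result is produced, all randomized-period efficacy, event, disposition and adverse event data are locked or frozen in an audit-trailed snapshot. Use that dataset for both the early look and the primary analysis, and document any later change with its reason. Cross-refer to this in 4.2.2.
2. Sign SAP Part 1 before that point, with the model terms, the interaction significance level and the pooling criterion fixed. If Part 1 already does this, cite it in 10.3.6. Define the interaction on the same split that the rule selects: randomization is stratified by any prior therapy (4.3), whereas first-line in 10.1 also includes treated subjects with less than a 10% relative FVC decline.
3. Release no first-line result by arm until the treatment-failure subgroup is also frozen.
4. Name who receives the results, and state whether statistics and data management staff are blinded until the freeze.

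**Cost.** Protocol wording, and a short delay to the early look and to the Section 9 decision. The length of the delay is not derivable from the documents; the snapshot option avoids waiting for a full lock. Alpha stays at 0.05, first-line subjects at 55 per arm, total enrolment at 136 and power at 80.9%.

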
Statistical Methods:
	
This study is planned to enroll approximately 136 subjects, who will include a target of 110 subjects who are seeking first-line therapy and approximately 26 subjects who failed pirfenidone and/or nintedanib treatment. First line therapy is defined as no prior therapy with pirfenidone and/or nintedanib or <10% relative decrease in FVC % predicted while receiving either pirfenidone or nintedanib. Pirfenidone and/or nintedanib failure is defined as having <math>\geq 10\%</math> relative decrease in FVC % predicted during prior pirfenidone and/or nintedanib treatment. The effect of first-line treatment is the primary interest of the study and is the basis for sample size estimates. Assuming a 10% dropout rate and a common standard deviation of 7.3, a sample size of 55 subjects per arm in the primary analysis population provides approximately 80% power to detect a treatment difference of 4.2 in change from baseline to Week 48 in percent predicted FVC, using a two-sample t-test at the two-sided significance level of 0.05. If the treatment effect in the pirfenidone and/or nintedanib treatment failure group is similar to that in the general population, the two subgroups will be combined to achieve higher power.
 
The primary efficacy analysis is to compare the treatment arms in change from baseline to Week 48 in FVC % predicted. A rank ANCOVA model will be used. A repeated measures model utilizing all observed data will be used for sensitivity analyses. Logistic regression and Fisher’s exact test will be used to compare categorical endpoints. The Cox regression model will be used in time-to-event endpoints. All efficacy and safety data will be summarized descriptively by treatment arm.

	Treatment effect will be evaluated in various subgroups of interest. Unblinded analyses will be performed after all subjects have either completed the Week 48 assessments or discontinued the study.
--	---

This study will be conducted in accordance with the guidelines of Good Clinical Practice (GCP) and the applicable regulatory requirement(s), including the archiving of essential documents.

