#### **4.3 Treatment Assignment**

Subjects are stratified by prior therapy with pirfenidone and/or nintedanib (yes/no) and randomized 1:1 to FG-3019 or placebo using an Interactive Web Response System (IWRS).

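### Section 10.3.6 permits the first-line and treatment-failure groups to be unblinded at different times with no testing order or alpha rule, which could raise the false-positive rate to about 7%.

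*Protocol*

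**What the plan says.** **Timing.** The synopsis (Statistical Methods) states: "Unblinded analyses will be performed after all subjects have either completed the Week 48 assessments or discontinued the study". The first sentence of Protocol Section 10.3.6 says the same for pulmonary function and fibrosis. The last sentence of that section then provides that, where there is a large gap between the two groups in completing enrolment, "unblinded subgroup analysis may be performed at different times". The size of gap that triggers this is not defined. Nor does the section say which group is read first, who sees the result, or what significance level applies.

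**Population.** Section 10.1 plans 110 first-line subjects and 26 who failed pirfenidone and/or nintedanib. It bases the sample size on first-line, treats second-line as exploratory, and adds that if the effects are similar "the two subgroups will be combined to achieve higher power". No criterion for similarity is given. Section 10.3.4.1 starts from the other end: the primary analysis is on the pooled full analysis set and moves to first-line only if the treatment-by-stratification interaction is significant. No level is stated for that interaction.

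**Alpha.** The only significance level given for an efficacy comparison is in the sample-size calculation, "using a two-sample t-test at the two-sided significance level of 0.05". SAP Part 2 covers the extension and plans no formal inference. It refers the randomized-period analyses to SAP Part 1, which is not supplied.

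**The concern.** The protocol gives two different times for the unblinded analysis and two candidates for the main population. Taken together, and without a stated order, they leave room for two positive claims: first-line when it is read, and the pooled set later if first-line falls short. Each could cite the same 0.05.

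Two things are at stake. One is the error rate, because a second chance at significance raises it above 5% unless an order or a split is fixed beforehand. The other is the conduct of the later part of the trial. If first-line is read first, the sponsor could hold the result for the group on which the trial is powered before the failure-group data are complete, and nothing in the documents supplied says who may see that group-level result.

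**Working it through.** **1. Reproduce the plan's own figure.** Inputs from Section 10.1: an effect of 4.2 points of FVC % predicted, dropout of 10%, and these planning values: "common standard deviation of 7.3, a sample size of 55 subjects per arm in the primary analysis population provides approximately 80% power". Section 4.3 gives allocation as "randomized 1:1 to FG-3019 or placebo".

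- t-test: 48.4, so 49 evaluable per arm; 49/0.90 = 54.4, so 55 enrolled per arm. This matches the plan.
- Power at 55 × 0.90 = 49.5 evaluable per arm: 80.9%.

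The sample size is sound for one test of first-line at 0.05.

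**2. Correlation between the two possible tests.** The first-line and failure groups share no subjects, but the pooled set contains all of first-line. With equal variances and w = 110/136 = 0.809, the pooled statistic is Zp = √w·Z1 + √(1−w)·Z2, where Z1 is first-line and Z2 is failures. Its correlation with Z1 is √0.809 = 0.90. Equal dropout in both groups leaves this unchanged (99/122.4 gives the same ratio).

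**3. False-positive rate with no true effect in either group.**

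- Either |Z1| or |Zp| above 1.96 (bivariate normal): 7.0%. In the favourable direction only, it is 3.5% instead of 2.5%. If between 120 and 100 of the 136 are first-line, the two-sided figure runs from 6.6% to 7.4%.
- With the Section 10.3.4.1 interaction rule, an interaction level must be assumed. The interaction statistic is √(1−w)·Z1 − √w·Z2. Results from 4 million simulated draws:

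| Assumed interaction level | Rule applied once | First-line first, then pooled if the interaction is not significant | Added by staging (points) |
|---|---|---|---|
| 0.05 | 5.5% | 6.9% | 1.4 |
| 0.10 | 5.8% | 6.8% | 1.1 |
| 0.15 | 5.9% | 6.7% | 0.8 |
| 0.20 | 6.0% | 6.6% | 0.6 |

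(The last column is taken from unrounded rates.)

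**4. How well the interaction test separates the groups.** With 49.5 and 11.7 evaluable per arm, the standard error is 7.3 × √(2/49.5 + 2/11.7) = 3.36. If the true effects were 4.2 in first-line and 0 in failures, the standardized difference would be 4.2/3.36 = 1.25, giving about 24% power at 0.05. A non-significant interaction is therefore weak evidence that the effects are similar.

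**5. Cost of the ways to hold 5%.**

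- Two equal tests need about 0.035 each (critical value 2.109). First-line power then falls from 80.9% to 76.5%. Restoring 80% takes about 54 evaluable per arm, and 54/0.90 = 60 enrolled instead of 55.
- First-line at 0.05, with no pooled claim unless first-line is significant: 5.0%, with no extra subjects.

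**The case against.** The strongest reply is that Section 10.3.6 prescribes nothing of the kind. It is a conditional permission, it sets no test and no level, and the two groups it separates are disjoint. A reader might infer that the protocol plans two 5% tests on overlapping data. It does not: the overlap arises only if a pooled analysis follows a first-line one and both are claimed. If the failure group were read first, the main result would not yet be known. Section 10.1 already calls second-line subjects exploratory, and SAP Part 1 may fix the order or the alpha. All of this stands, and it limits the claim to what could happen. It does not remove the conflict within the protocol.

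Three other readings go further than the documents allow.

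- *Staging turns a blind pooling decision into an unblinded one.* Both pooling rules (similar effects in Section 10.1, the interaction in Section 10.3.4.1) need treatment-group data, so pooling would use unblinded data even in a single analysis. Staging adds only early knowledge of the first-line result.
- *Those who have seen the early result could then enlarge the trial under Section 8.1.* That section leaves an increase to the sponsor and ties it to projected dropout above 10%, not to efficacy. It does not say that the same people do both.
- *Site judgements in the later group would be biased.* Section 4.4.3 keeps investigators, subjects and study teams blinded until the study is complete and withholds individual assignments at planned efficacy assessments. Bias would need a leak of the group-level result. The judged events, clinical progression and intercurrent illness, enter progression-free survival and not the primary FVC endpoint. What remains open is access to group-level results, which nothing supplied restricts.

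**Conclusion.** The concern holds in a limited form. The last sentence of Section 10.3.6 conflicts with that section's first sentence and with the synopsis. Because Sections 10.1 and 10.3.4.1 name different main populations and the documents supplied give no order, a staged analysis could support two claims at 0.05. The false-positive rate could then reach about 7.0%, or 6.9% with the interaction rule at an assumed 0.05 level.

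The rise is moderate. Part of the excess over 5% comes from the Section 10.3.4.1 switch rule and would be there without staging; staging itself adds about 1.4 points, and less at higher assumed interaction levels.

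These figures assume that first-line is read first, that either result counts as success, that variances are equal, and that there is no effect in either group. They also take the 110/26 split as the interaction factor. The randomization stratum is prior therapy yes/no (Section 4.3), and first-line also includes treated subjects with less than a 10% relative decline (Section 10.1), so the protocol's own interaction is not exactly the one modelled. SAP Part 1 could change the conclusion on alpha and order, but not the contradiction in timing.

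**What to change.** **Preferred.** Delete the last sentence of Section 10.3.6, so that there is one unblinded efficacy analysis at the time the synopsis gives. This is a one-sentence change. Its cost is that the first-line result may wait for the slower group. Deletion alone does not restore 5%: the switch rule in Section 10.3.4.1 still gives about 5.5% (up to 6.0% across the assumed interaction levels). Naming first-line, as defined in Section 10.1, as the sole 0.05 test removes that excess too, and Section 10.3.4.1 would need to be aligned with it.

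**If staging is kept.** Before any unblinding:

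- State that first-line is the only 0.05 test and that every later pooled or failure-group result is exploratory. This holds 5% with the planned 55 per arm.
- Keep the early group-level result from anyone running the failure group or reviewing its data.

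The cost is that the pooled analysis loses confirmatory status. If SAP Part 1 already fixes these points, the protocol should refer to it and the timing sentences should be made to agree.
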